7.5.5. Progression-free Survival

Progression-free survival is defined as the time from the date of first dose of study drug to the earliest date of disease progression, as determined by IRR and investigator per RECIST v1.1, or death due to any cause, whichever occurs first, and will be summarized in months:

$$\text{PFS (months)} = [(\text{date of event or censoring} - \text{date of first dose}) + 1] / 30.4375.$$

Participants without an event or with an event more than 16 weeks (for the first 12 months after treatment start date) or 24 weeks (after the first 12 months of treatment start date) after the last adequate tumor assessment will be censored on the date of the last adequate tumor assessment that documented no progression. In addition, if a new anticancer therapy is started prior to an event, the participant will be censored on the date of the last adequate tumor assessment that documented no progression prior to the start of the new anticancer therapy. Note: if date of progression occurs on the same date as the start of new anticancer therapy, the progression will be counted as an event.

An adequate post-baseline assessment is defined as an assessment where a response of CR, PR, SD, non-CR/non-PD, or PD can be determined. Time points where the response is NE or no assessment was performed will not be used for determining the censoring date.

Participants with no baseline tumor assessment (including participants with an inadequate baseline assessment) or with no adequate post-baseline tumor assessments within 16 weeks after treatment start date will be censored on the day of treatment start date, unless the participant dies within 16 weeks of treatment start date, in which case, death will be an event on date of death.

The censoring and event date options to be considered for the PFS analysis are presented in Table 4.

Table 4. PFS Outcome and Event Dates

Situation	Date of Progression/Censoring	Outcome
No adequate baseline assessment	Date of treatment start date ^a	Censored ^a
PD or death ≤ 16 (or 24) ^b weeks after last adequate tumor assessment or ≤ 16 weeks after treatment start date	Date of PD or death	Event
PD or death > 16 (or 24) ^b weeks after the last adequate tumor assessment ^c	Date of last adequate tumor assessment ^c documenting no PD prior to new anticancer therapy or missed assessments	Censored
No PD		
New anticancer therapy given		

^a If the participant dies ≤ 16 weeks after treatment start date, the death is an event with date on death date.

^b Durations are equal to 2 times the length of the tumor assessment interval, which is 16 weeks for the first 12 months after treatment start date, and 24 weeks thereafter.

^c If there are no adequate post-baseline assessments prior to the PD or death, then the time without adequate assessment should be measured from treatment start date; if the criteria is met, the censoring will be on treatment start date.

An estimate of the PFS survival function will be constructed using the KM method (Kaplan & Meier, 1958³) as implemented in PROC LIFETEST. The 25%, median, and 75% DOR (in months) will be summarized along with 95% confidence intervals as calculated from the PROC LIFETEST output (using method of [Brookmeyer & Crowley, 1982¹]).

Frequency counts and percentages of participants with each event type (PD or death) and censoring reasons will be summarized. Censoring reasons are as follows:

- Ongoing in the study without an event
- No adequate baseline assessment
- No adequate post-baseline assessment
- New anticancer therapy was given
- Progression or death after 2 or more missed assessments
- Withdrawal of consent
- Lost to follow-up

If a participant meets multiple definitions for censoring the list below will be used to define the hierarchy.

Table 5. Censoring Reasons and Hierarchy

Hierarchy	Condition	Censoring Reason
1	No adequate baseline assessment	No adequate baseline assessment
2	Start of new anticancer therapy before event.	Start of new anticancer therapy
3	Event after 2 or more missing or inadequate postbaseline tumor assessment	Event after missing or inadequate assessments ^a
4	No event and [withdrawal of consent date \geq , date of first dose OR End of study (EOS) = Participant refused further follow-up]	Withdrawal of consent
5	No event and lost to follow-up in any disposition page	Lost to follow-up
6	No event and [EOS present OR any disposition page after screening says participant will not continue into any subsequent phase of the study] and no adequate postbaseline tumor assessment	No adequate postbaseline tumor assessment
7	No event and none of the conditions in the prior hierarchy are met	Ongoing without an event

a .More than 16 weeks after last adequate tumor assessment.

A graph of the estimated KM curve will be presented.

In addition, time to progression/censoring, event and censoring reasons will be listed.

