7.1.8. Tumor assessment dates

Tumor assessment dates will be assigned differently for IRR assessment and for investigator’s assessment of tumor data.

For analyses of IRR assessments, the date of tumor assessments will be provided by IRR and identified as the earliest scan/assessment date at each nominal timepoint. These dates, together with the determined overall tumor response at each timepoint, will be used to programmatically identify the response/progression date and for censoring in time to event analyses.

For analyses based on investigator's assessment, response/progression are derived programmatically from the target lesions measurements, non-target lesions status, and new lesions recorded on the eCRF, and the date of tumor assessment will be derived as the earliest scan/assessment date.

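### The PFS and DOR gap rule can censor a progression found after one missed scan, although the SAP describes it as two or more missed assessments; the treatment-start censoring sentence also contradicts Table 4

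*SAP*

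**What the plan says.** **Gap rule.** SAP 7.5.5 censors "Participants without an event or with an event more than 16 weeks (for the first 12 months after treatment start date) or 24 weeks" past the last adequate scan. Table 4 uses the same cut, and its footnote b gives the basis: "Durations are equal to 2 times the length of the tumor assessment interval". SAP 7.5.2 applies the PFS censoring rules to DOR.

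**Description of the rule.** The list of censoring reasons in 7.5.5 names the category "Progression or death after 2 or more missed assessments". The condition in Table 5 row 3 is "Event after 2 or more missing or inadequate postbaseline tumor assessment". The reason shown in that row carries footnote a: "More than 16 weeks after last adequate tumor assessment".

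**Treatment-start rule.** A sentence in 7.5.5 says that participants with "no adequate post-baseline tumor assessments within 16 weeks after treatment start date will be censored on the day of treatment start date", the only exception being death within that period. Table 4 footnote c is narrower. Only if no adequate post-baseline scan precedes the progression or death, "then the time without adequate assessment should be measured from treatment start date".

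**Scan timing.** Protocol 7.2.3 schedules scans every 56 days, ±7 days, for 12 months and every 12 weeks, ±7 days, after that, on a fixed calendar. Under SAP 7.1.8 the IRR scan date is "identified as the earliest scan/assessment date at each nominal timepoint". The investigator scan date is also the earliest scan date, but that paragraph mentions no nominal time point.

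**The concern.** The cut is an elapsed time, while the label is a count of missed scans. The two agree only if scans fall on their nominal days. Once actual dates within a ±7-day window are used, progressions with the same scan history (one scan missed, the next done in window) are counted or censored according to where in their windows the two scans fell. Censoring a real progression at the earlier scan moves the Kaplan-Meier curves for PFS and DOR upward, and neither 7.5.2 nor 7.5.5 plans a sensitivity analysis of this rule.

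The treatment-start sentence raises a different problem. Two programmers could code the same participant differently, one as an event at the observed progression and the other as contributing no PFS time at all.

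**Working it through.** Gaps below are simple date differences in days.

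**1. The SAP's own figures.** 2 × 8 = 16 weeks = 112 days, and 2 × 12 = 24 weeks = 168 days. Both agree with footnote b.

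**2. In-window gaps.** Let I be the scan interval (56 or 84 days), k the number of missed scans, and a and b the offsets of the earlier and later scan from their nominal days, each a whole number from −7 to +7. Then gap = (k + 1) × I + (b − a), over 15 × 15 = 225 pairs.

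| Missed scans | 8-weekly gap | Over 112 | 12-weekly gap | Over 168 |
|---|---|---|---|---|
| 0 | 42–70 | 0/225 | 70–98 | 0/225 |
| 1 | 98–126 | 105/225 | 154–182 | 105/225 |
| 2 | 154–182 | 225/225 | 238–266 | 225/225 |

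With one missed scan, the cut is exceeded exactly when b > a, which gives (225 − 15)/2 = 105 pairs. That is 46.7% if all days in the window are equally likely (an assumption). If 50%, 75% or 100% of scans are placed on the nominal day and the rest spread evenly, the share is 35.0%, 20.4% or 0%. If scans after a miss run 0 to 7 days late, it is 70–83%.

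**3. Progression at the first adequate scan, week 8 missed.** The gap from treatment start is 112 + b, so 7 of the 15 window days exceed 112. Here the sentence and footnote c agree on censoring at treatment start, after one missed scan.

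**4. Deaths.** Take deaths spread evenly between closure of the first and of the second missed window. The share over the cut is 105/840 = 12.5% (8-weekly) or 105/1260 = 8.3% (12-weekly), so deaths are less affected.

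**5. Table 5.** A one-miss progression at 113–126 or 169–182 days does not meet the row 3 condition, and rows 4 to 7 require no event. It does meet footnote a. That footnote gives 16 weeks only. After month 12 every in-window one-miss progression (154–182 days) exceeds 112 days, whereas Table 4 counts those up to 168 days.

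**6. Month 12.** The SAP does not say whether the event date or the last-scan date selects the 16- or 24-week limit. Assume 12-weekly scans are counted from week 48.
- Last scan week 48, week 60 missed, progression at week 72: 225/225 pairs are censored under 16 weeks, 105/225 under 24.
- Last scan week 40, week 48 missed, progression at week 60 (126–154 days): 225/225 under 16 weeks, 0/225 under 24.

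**7. Treatment-start sentence against Table 4.** Days are counted after treatment start.
- Week 8 missed; stable disease at 115 days (inside the week-16 window of 105–119 days); progression at 168 days. The sentence censors at treatment start. Table 4 sees a gap of 168 − 115 = 53 days and counts an event.
- Weeks 8 and 16 missed; stable disease at week 24 (168 days); progression at week 32 (224 days). The sentence again censors at treatment start. Table 4 sees 56 days and counts an event.
- If that first scan is a partial response, later confirmed, the participant is a responder with no PFS time. Applied literally to DOR, the censoring date would precede the response.

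**8. Illustrative size of the gap rule.** If 5–15% of progressions follow exactly one missed scan (assumed), then 0.05 × 105/225 = 2.3% to 0.15 × 105/225 = 7.0% of progressions are censored against the label.

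A simulation compared the current rule, cut chosen by event date, with counting scheduled scans. It used exponential medians of 10.9 and 10.2 months (PFS) and 10.4 and 9.0 months (DOR) from Protocol 2.1.2, and 24 months of follow-up. It assumed 3–10% of scans missed and symmetric scatter ranging from uniform to 75% on the nominal day.
- 12-month PFS was 0.3–2.1 points higher under the current rule, and 12-month DOR 0.2–1.6 points higher.
- With 25% of progressions found on symptom-driven scans and 10% of events being deaths (medians 10.9 and 10.4 only), PFS was 0.2–1.5 points higher.
- With scans running late after a miss (same two medians), PFS was 1.1–3.2 points higher.

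For scale, the standard error of 12-month PFS is √(0.47 × 0.53/n), or 6.4 points at n = 60 and 8.2 at n = 37, with complete follow-up assumed.

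**The case against.** The strongest reply is that the operative rule is clear. The text, Table 4 and footnote b all give the same 16- and 24-week cut, and the reference to two missed assessments is shorthand. Changing the label would cure the mismatch without altering any estimate. That is true of the wording. It would still leave inclusion of a progression dependent on scan dates within the permitted window, and it would not repair footnote a or the treatment-start sentence.

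Table 4 is also introduced, shortly after that sentence, as the set of options for the PFS analysis, so it arguably governs. The SAP states no order of precedence, however.

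Several limits on the effect stand. Protocol 7.2.3 says scans should keep to the calendar, and Protocol 7.2.1 allows symptom-driven scans, which shorten gaps. Censoring reasons will be tabulated and listed, so cases can be traced. The final treatment-naïve ORR analysis comes 14 months after the last such enrollment, so 24 months of follow-up may not apply to everyone if PFS is reported then.

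A reader might infer that a censored one-miss progression has no place in Table 5. The documents do not support that, because footnote a covers any gap over 16 weeks; the row 3 condition is what it fails. A reader might also take 105/225 to mean that nearly half of progressions after a missed scan will be lost. It is a share of date pairs, and the documents say nothing about how often each pair occurs.

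**Conclusion.** The point holds as an internal contradiction in the SAP. As written, the gap rule does not deliver its label: a progression found in window after one missed scan is censored whenever the later scan sits later in its window. Footnote a contradicts the 24-week limit. The treatment-start sentence contradicts Table 4 and footnote c for any participant whose first adequate scan without progression comes more than 16 weeks after start.

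The gap rule acts upward on PFS and DOR and is probably small. The documents cannot size it, since they give neither a missed-scan rate nor a scan-timing distribution; the figures in step 8 rest on assumed values, and the effect is zero if every scan is on its nominal day. I assign no direction to the treatment-start conflict.

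It would be wrong to infer that the study's main conclusion is at risk. PFS and DOR are descriptive secondary endpoints, and the ORR test does not use this rule. The correction is still worth making before database lock, because the rules as written censor real progressions and, on one reading, erase observed PFS time.

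**What to change.** - **Gap rule.** Censor a progression or death only when two or more consecutive scheduled assessments, with their windows closed, have no adequate assessment before the event. Count from treatment start if there is no adequate post-baseline scan. Apply the same rule to DOR.
- **Time points.** State the nominal scan weeks around month 12, and say how unscheduled scans and investigator-assessed scans are assigned to time points. SAP 7.1.8 gives nominal time points only for IRR. Counting also removes the need to choose between 16 and 24 weeks around month 12.
- **Treatment-start sentence.** Replace it with the Table 4 and footnote c rule, so that a late first adequate scan followed by progression is judged by the gap before that progression.
- **Table 5.** Align the row 3 condition and footnote a with the same rule.

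Lengthening the cut to 18 and 26 weeks (126 and 182 days) would separate one missed scan from two for in-window progressions. It is less clean for deaths: after two closed missed windows, 105/840 (8-weekly) or 105/1260 (12-weekly) of deaths in the following interval would still count as events.

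The cost is SAP wording and a modest time-point counter in programming, with no new data. A few more events may be counted, so PFS and DOR may look slightly less favorable.

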
- Unacceptable AEs or failure to tolerate study treatment is defined as:
 - Grade 4 or life-threatening AE as outlined in Appendix 2 and Appendix 3, (except with approval from the Sponsor);
 - Toxicity requiring more than the allowed number of dose reductions for encorafenib and binimetinib as described in Table 7 and Table 8, respectively;
 - Occurrence of an AE that is related to study treatment and in the judgment of the Investigator compromises the patient's ability to continue study-specific procedures, or is considered to not be in the patient's best interest.
- Patient has missed > 6 weeks (i.e., 42 consecutive days) of dosing per Section 6.6.1.
- Disease progression per RECIST v1.1.
- Clinical progression, as determined by the Investigator in the absence of radiographic progression.
- Patient becomes pregnant or begins breastfeeding.
- Significant protocol deviation that, in the opinion of the Investigator and/or Sponsor, renders the patient unsuitable for further study treatment administration.
- Patient is noncompliant with study procedures or study treatment that in the judgment of the Investigator or Sponsor renders the patient unsuitable for further study participation.
- Patient is lost to follow-up.
- Death.
- Termination of the study by the Sponsor (described in Section 4.6 and Section 9.10). Version 5 Pfizer Confidential

If the decision is made to permanently discontinue study treatment the EOT visit should be conducted (see Section 7.1.3). Reasonable efforts should be made to have the patient return for all applicable follow-up visits (safety and efficacy), as outlined in the Table 3. The date of the last dose of study treatment will be recorded in the eCRF.

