7.2. Efficacy Assessments

7.2.1. Radiological Tumor Evaluation

RECIST v1.1 (Eisenhauer et al, 2009) will be applied by the site as the primary measure of tumor assessment and response and as the basis for protocol guidelines related to disease status (e.g., discontinuation of study treatment).

Radiological scans of all suspected sites of disease will be performed utilizing the same method and technique throughout the study. Target lesions should demonstrate the patient's baseline tumor burden and will be selected based on size (i.e., lesions with the longest diameter), and suitability for accurate repeat assessment.

The following should be performed:

- Chest, abdomen, and pelvis CT scans (or MRI if CT is contraindicated) scans are required for all patients at Screening. An MRI of the brain is also required for all patients at Screening. A CT scan of the brain, preferably with IV contrast, may be performed if MRI is contraindicated. Additional imaging of anatomical sites (e.g., head and neck, etc.) should be performed as applicable based on location of disease sites.
- During the study chest, abdomen, and pelvis CT scans (or MRI if CT is contraindicated) are required for all patients. If additional imaging of anatomical sites (e.g., head and neck) were performed at baseline, they should be continued throughout the duration of the study. Additional imaging of anatomical sites (e.g., head and neck, etc.) should be performed as applicable based on location of disease sites. Subsequent MRIs of the brain will only be performed if there were lesions present at baseline.
- Skeletal lesions identified at Screening should continue to be imaged at subsequent scheduled visits using localized CT, MRI, or X-ray (using the same method used at Screening for all visits for any given lesion).
- Additional imaging evaluations may be performed at any time if there is symptomatic evidence suggesting the possibility of disease progression based on clinical symptoms or physical examination. If off schedule imaging evaluations are performed in the absence of progression, every effort should be made to perform subsequent imaging evaluations in accordance with the original imaging schedule or discussed with the Sponsor as applicable.

Chest X-ray or ultrasound should not be used for tumor response assessments in this study.

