7.2.3. Tumor Imaging During Treatment

The first imaging assessment should be performed as follows:

- 8 weeks after the first dose of study treatment
- Every 8 weeks (56 days ± 7 days) for 12 months, and then every 12 weeks (± 7 days) thereafter until disease progression is determined or until any of the criteria in Section 7.1.4.2 are met.
- Imaging assessments may be performed more frequently if clinically indicated.

Imaging should follow calendar days and should not be delayed, irrespective of study treatment administration (i.e. delays in cycles or dose holds).

Per RECIST v1.1, responses (PR or CR) should be confirmed by a repeat radiographic assessment. The scan for confirmation of response may be performed no sooner than 4 weeks after the first documented response and no later than the next per-protocol scheduled scan, whichever is clinically indicated.

Radiographic disease assessments should be performed until disease progression per RECIST v1.1, withdrawal of consent, initiation of subsequent anticancer therapy, patient is lost to follow-up, death or defined end of study (see Section 4.5 and Section 6.8).

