7.2.4. Independent Radiology Review

All radiographic images from screening and performed during the study are to be sent to a central imaging vendor to perform an independent radiographic imaging assessment of tumor status. Further details of the IRR are described in the Independent Radiology Review Charter. A detailed description of the procedures for the collection and storage of radiological scans is provided in the Study Manual. Of note, patient management decisions will be made by Investigator assessment and not by the independent central review. Results from IRR will not be provided to the Investigator.

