7.5.2. Duration of Response

DOR is defined as the time from the date of the first documented response (CR or PR) that is subsequently confirmed, to the earliest date of disease progression, as determined by IRR and investigator per RECIST v1.1, or death due to any cause. If a participant with a CR or PR has neither progressed nor died at the time of the analysis cutoff or at the start of any new anticancer therapy, the participant will be censored at the date of last adequate tumor assessment. The same rules used for censoring of PFS will be applied, see [Section 7.5.5](#) for more details. DOR will be calculated for participants who have achieved a confirmed response (i.e., CR or PR).

An estimate of the DOR survival function will be constructed using the KM method (Kaplan & Meier, 1958³) as implemented in PROC LIFETEST. The 25%, median, and 75% DOR (in months) will be summarized along with 95% confidence intervals as calculated from the PROC LIFETEST output (using method of [Brookmeyer & Crowley, 1982¹]).

Frequency distribution (<3 months, ≥3 months, ≥6 months, ≥9 months, ≥12 months, ≥24 months) will be provided.

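### Scheduled scans end at the site's RECIST progression, but the main PFS and DOR analyses count only IRR progression; the resulting censoring is informative and SAP Table 5 can label it as ongoing

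*SAP*

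**What the plan says.** **Who decides progression and when scans stop.** Protocol 7.2.1 states that RECIST v1.1 "will be applied by the site as the primary measure of tumor assessment and response and as the basis for protocol guidelines". Protocol 7.2.3 adds: "Radiographic disease assessments should be performed until disease progression per RECIST v1.1, withdrawal of consent, initiation of subsequent anticancer therapy", and lists further stopping reasons. Under Protocol 7.1.3 and 7.1.4.2, post-treatment scans are only for patients who stopped treatment for a reason other than disease progression.

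**What IRR does.** Protocol 7.2.4 says that "patient management decisions will be made by Investigator assessment and not by the independent central review", and "Results from IRR will not be provided to the Investigator".

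**What the analysis counts.** Protocol 8.4 bases the primary analyses of tumour endpoints on IRR and adds sensitivity analyses by investigator. SAP Appendix 1 derives IRR progression from the date that IRR reports. SAP 7.5.5 censors a patient without an event at the last adequate assessment showing no progression. For DOR, SAP 7.5.2 says: "The same rules used for censoring of PFS will be applied".

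**How censoring is labelled.** Table 5 in SAP 7.5.5 has seven rows. The last is the residual, "No event and none of the conditions in the prior hierarchy are met", and its reason is *Ongoing without an event*. No row names investigator or clinical progression.

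**Clinical progression.** Protocol 6.7 lists "Clinical progression, as determined by the Investigator in the absence of radiographic progression" as a reason to stop treatment, separately from RECIST progression.

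**The concern.** One reader decides when observation ends and a different reader supplies the event. When the two disagree on a scan, the patient leaves scheduled imaging because the site judged the tumour to be growing. IRR then has no later scheduled scan on which to agree. Kaplan-Meier estimation treats a censored patient as having the same future risk as those still observed, and here that is unlikely to be true. The direction is towards longer IRR PFS and DOR.

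This is a single-arm trial, so no control arm offsets the bias. DOR is the evidence on durability, and Protocol 4.2 supports the choice of ORR by citing approvals in which the responses were also durable. A censoring table that calls such patients ongoing would hide the mechanism from the reader.

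**Working it through.** **1. The plan's own figures.** Table 4 sets its gap limit at twice the scan interval: 2 × 8 = 16 weeks in the first 12 months and 2 × 12 = 24 weeks after. These reproduce. The ORR rules also reproduce by exact binomial: at least 32 of 60 gives one-sided alpha 0.0170 and power 0.977 (39% versus 65%); at least 13 of 37 gives 0.0231 and 0.916 (20% versus 45%). None of this depends on the PFS censoring rules.

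**2. One patient traced through the rules.** At a scheduled scan the investigator calls RECIST progression and IRR reads the same scan as stable. Treatment stops (Protocol 6.7) and scheduled scans stop (7.1.4.2, 7.2.3). The site cannot know that IRR disagrees (7.2.4). In the IRR analysis this scan is the last adequate one. The possible outcomes in SAP Tables 4 and 5 are:

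- death within 16 (24) weeks of that scan, no new therapy: event;
- new anticancer therapy: censored, row 2;
- death after the gap limit: censored, row 3;
- consent withdrawn or lost to follow-up: rows 4 and 5;
- everything else: row 7, ongoing.

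Row 6, which covers patients with an end-of-study record, also requires that there be no adequate post-baseline scan. A patient who left the study after an adequate scan therefore falls through to row 7. For DOR, row 6 can never apply, because every confirmed responder has adequate post-baseline scans.

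**3. What the investigator-based analysis adds.** It counts the site's radiographic progression as an event. It derives progression from lesion data on the eCRF (SAP 7.1.8, 7.5), so clinical progression without lesion change is not an event there either. Table 3 compares IRR and investigator on response only, so the number of patients discordant on progression would not be reported.

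**4. Size, as an illustration.** The documents give no discordance rate. The assumptions are:

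- exponential PFS with median 10.9 months, the treatment-naïve figure cited in Protocol 2.1.2;
- scans every 8 weeks to week 56, then every 12;
- in discordant patients, investigator progression comes one scan before IRR would have called it; progression before the first scan cannot be discordant;
- 40% or 70% of discordant patients start new therapy;
- median time to death for the others is 26 weeks.

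Check of the reference value: 10.9 × 30.4375 / 7 = 47.4 weeks, and 0.5^(56/47.4) = 0.44.

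| Discordance | Week-56 PFS, scans continue to IRR progression | SAP rule | Difference (points) | Investigator progression as event |
|---|---|---|---|---|
| 10% | 0.44 | 0.464–0.468 | 2.4–2.6 | 0.433–0.435 |
| 20% | 0.44 | 0.490–0.498 | 4.9–5.7 | 0.427 |
| 30% | 0.44 | 0.519–0.528 | 7.8–8.7 | 0.420 |
| 40% | 0.44 | 0.547–0.564 | 10.6–12.2 | 0.412–0.414 |

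With a median of 10.2 months (the previously treated figure), the reference is 0.42 and the differences are 2.4–2.7 points at 10% and 5.0–5.8 at 20%. A fixed time point is used because simulated medians jump from one scan date to the next.

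With median 10.9 months and a 26-month cutoff, the discordant patients split as: row 2, 39–70%; death counted as an event, 11–23%; row 3, 12–25%; row 7, 6–13%.

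**The case against.** The strongest reply is that investigator-based PFS and DOR are already planned, and they count the site's radiographic progression. That is correct, and it means the affected group is not invisible. It does not repair the IRR estimate, which is the main one. Nor does it show how many IRR censorings follow an investigator call.

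Second, few patients reach row 7: in the illustration only 6–13% of the discordant group. This stands for the label. It does not remove the bias, because patients in rows 2 and 3 are also censored at a scan on which the site had already called progression.

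Third, the list of reasons in SAP 7.5.5 speaks of being ongoing in the study, and a patient in survival follow-up is still in the study. That is fair for those patients, although their disease assessment has ended. It fails for patients with an end-of-study record. SAP 7.5.6 has a separate OS category for patients no longer followed; PFS has no counterpart.

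A reader might also infer that scanning stops at clinical progression. No passage says so. Protocol 6.7 lists it apart from RECIST progression, Protocol 7.2.3 ties the end of scanning to RECIST, and the Schedule of Activities and SAP 4.1 continue scans when the reason was not PD. Protocol 7.1.3 and 7.1.4.2 use the looser term, so the text is ambiguous but leans towards continued scans.

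A reader might further multiply the median by 1/(1 − f), where f is the share of progressions lost. On the cited treatment-naïve median DOR of 10.4 months this gives 10.4/0.9 = 11.6 or 10.4/0.8 = 13.0 months. The documents supply no f, and the shortcut ignores deaths that count as events. Applied to week-56 PFS it gives 0.44^0.9 = 0.48 and 0.44^0.8 = 0.52, above the simulated 0.46–0.47 and 0.49–0.50.

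**Conclusion.** The point holds for investigator-assessed RECIST progression without IRR progression. Such patients have no further scheduled scans. Unless a timely death without new therapy counts, the IRR analyses of PFS and DOR censor them informatively. Some of them, including patients who have left the study, are then labelled as ongoing.

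The documents do not support saying that all such patients are censored, that all are labelled ongoing, or that the investigator-based analyses miss them.

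The effect is on secondary endpoints that carry no hypothesis or power; the primary ORR test is unaffected. The direction follows from the rules if the site's calls tend to precede true progression. The size does not follow from the documents: roughly 2 to 6 percentage points on week-56 PFS at 10–20% discordance rests on assumed discordance, new-therapy and death rates.

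**What to change.** 1. **SAP 7.5.5, Table 5 and the list of censoring reasons.** Add above row 7 a reason such as *Investigator or clinical progression without IRR progression*, and a reason for patients who left the study with an adequate post-baseline scan. Restrict the ongoing label to patients still under disease assessment.
2. **SAP 7.5.2 and 7.5.5.** Add a prespecified sensitivity analysis of IRR DOR and PFS in which stopping treatment for investigator or clinical progression without IRR progression is an event on that date. In SAP 7.5.1, extend the disagreement summary from response to progression.
3. **Passages to reconcile.** Disease progression in Protocol 7.1.3 and 7.1.4.2 needs to be squared with the RECIST wording in 7.2.3 and with the wording on PD in the Schedule of Activities and SAP 4.1. Separately, Protocol 6.5.2 treats palliative radiation as clinical progression for PFS, while SAP 7.1.7 treats subsequent radiation as new therapy, which censors. The sponsor should settle which reading applies.

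The cost is some SAP wording, one additional analysis from disposition data already summarised under SAP 7.2, and a clarification in the protocol. The sensitivity medians will be somewhat shorter than the main ones. The primary test and the sample size do not change.
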